Over the years, an increased understanding of how a child's physiology interacts with a ventilation system has led to improved technologies. Whereas traditional ventilation modalities such as endotracheal intubation is invasive and can lead to tracheal damage with prolonged use (3), non-invasive ventilation (NIV) modalities avoid the risks associated with tracheal intubation. In addition, NIV can be used at an earlier stage compared to tracheal intubation, and facilitates gradual weaning when used intermittently (4). Two modalities that are widely used in intensive care units are continuous positive air pressure (CPAP) and bilevel positive air pressure (BiPAP). Both of these modalities operate using positive airway pressure to keep the trachea open. CPAP machines are set to deliver a continuous stream of air, while BiPAP machines offer a different level of pressure for inhalation versus exhalation. Collectively, use of these modalities and their benefits are well-documented, including improved gas exchange, decreased respiratory and heart rate, and decreased inspiratory work of breathing (5-8). Building on these strengths, neurally adjusted ventilator assist (NAVA) is emerging as an alternative form of the bi-level NIV with application in multiple settings.

With NAVA support, delivery of positive pressure is based on the electrical activity of the diaphragm (Edi) via a nasogastric (NG) catheter that is placed on the phrenic nerve, which runs along the esophagus. This concordance between the Edi and NAVA lends itself to synchrony between the patient and ventilator, as well as respiratory support that is proportional to the neural effort of the patient (9). Synchronous ventilation support results in decreased neural drive and

improved comfort in intubated patients (10, 11). Prior research has examined the use of NAVA in different patient settings, most notably the PICU and NICU as summarized in **Table 1**. These studies suggest NAVA may contribute to decreased sedation needs (12), improved synchrony (10, 13, 14), improved breath-to-breath mechanical variability (10), increased patient comfort (10), and reduction of wasted breathing efforts (13). In these populations, evidence supports the safety and feasibility of NAVA (12, 15).

Reference	Setting	Design	Intervention	Results
Kallio et	PICU	Randomized	Conventional ventilation (CV)	Ventilation duration: 3.3hrs NAVA and 6.6hrs
al 2014		controlled trial	or NAVA	CV (P=0.17); Sedation amount: 0.80units/hr
				NAVA and 2.23units/hr CV (P=0.03, excluding postoperative patients)
Ducharme	PICU	Non-	Conventional NIV (CNIV)	Asynchrony index: 8% NAVA and 27/32%
-Crevier et		randomized,	[30mins], NAVA [60mins],	CNIV (P=.05); Wasted efforts: 0% NAVA and
al 2015		Crossover	CNIV [30mins]	12/6% CNIV (P<.01)
De la	PICU	Non-	Conventional PS ventilation	Asynchrony index: 2.0% NAVA and 8.5/7.5%
Olivia et		randomized,	[10mins], optimized PS	optimized PS (P=0.017/0.008); COMFORT
al 2012		Crossover	[10mins], NAVA [10mins],	score: 15 NAVA and 18/17.5 optimized PS
			optimized PS [10mins]	(P=0.0125/0.039)
Lee et al	NICU	Randomized,	Conventional PS ventilation	Trigger delay: 35.2ms NAVA and 294ms PS
2015		Crossover	[5mins], NAVA [5mins]	(p<0.001); Inspiratory time in excess: 32.3%
				NAVA and 294.6% PS (p=0.001)

Table 1. Selected prior NAVA studies in the PICU or NICU

While many studies have examined NAVA in the PICU and NICU, there is a paucity of research in the cardiovascular intensive care unit (CVICU) setting. PICU and NICU patients often are critically ill with diseased or malfunctioning lungs, but relatively healthy hearts. Conversely, CVICU patients have abnormal hearts with relatively healthy lungs. Given the implications for improved cardiopulmonary interactions (16), NAVA could be beneficial in the CVICU. The use of NAVA in the pediatric CVICU has been described in one article, which compared the use of cPAP versus NAVA in infants < 5 kg following postoperative extubation. The 2015 randomized cross-over trial found that the synchronization rate using NAVA was 99.3% for all respiratory cycles, and EAdi measurements suggest that NAVA decreased the work required to breathe more quickly than nasal cPAP (17). This study focused on proximal measurements of NAVA effectiveness, but more research is needed to understand how NAVA affects the clinical course of CVICU patients. To the investigator's knowledge, no studies to date have examined clinical outcomes in pediatric patients postoperatively in the CVICU. Understanding clinical outcomes following NAVA use could further inform use of the relatively new technology in this clinically complex patient population.

NAVA has recently been adopted for non-invasive respiratory support in the Children's Hospitals and Clinics of Minnesota CVICU, the cardiovascular care center (CVCC). Close to 10% of CVCC post-operative patients receive a form of bi-level NIV support, either NAVA or BiPAP. The frequency of NIV use in neonates (0 to 28 days of age) can be 30% or higher. We propose a randomized study to compare clinical outcomes following use of NAVA versus BiPAP in CVCC patients following cardiac surgery. Specifically, we will compare duration of NIV, duration of sedation, and hospital length of stay.

Research Question

Is the use of synchronized biphasic support with NAVA associated with shorter duration of noninvasive respiratory support, less sedation requirements, and reduced hospital length of stay compared to conventional BiPAP?

4. Study Design and Methodology

Aim 1: To assess whether the use of neurally adjusted ventilator assist (NAVA) is associated with a shorter duration of non-invasive respiratory support compared to conventional BiPAP. **Aim 2:** To assess whether the use of neurally adjusted ventilator assist (NAVA) is associated with less sedation requirements compared to conventional BiPAP.

Aim 3: To assess whether the use of neurally adjusted ventilatory assist is associated with reduced hospital length of stay compared to conventional BiPAP.

Hypothesis: Synchronized biphasic support with NAVA will be associated with shorter duration of non-invasive respiratory support, less sedation requirements, and reduced hospital length of stay.

Overview/Scope

Study Design

This will be a prospective randomized study comparing outcomes of pediatric patients who are treated with NAVA versus BiPAP respiratory support following cardiac surgery. Subjects will include pediatric CVCC patients who undergo cardiac surgery from October 2016 through October 2017 and who are up to 12 months of age. As patients recover from cardiac surgery, they are extubated and may require further respiratory support. If so, they receive CPAP support and then are transitioned to one of two modalities: either NAVA or BiPAP support. Both modalities are routinely used in the Children's CVCC, and the investigators will compare if one modality produces more favorable outcomes than the other. Following CPAP, enrolled subjects will be randomized to receive either NAVA or BiPAP, and their remaining clinical course will follow standard care. Specific measures following initiation of respiratory support will be collected, in addition to characteristics of the operative procedure and patient diagnoses. The study aims to compare duration of respiratory support, sedation requirements, and hospital length of stay between the two modalities.

Time Frame/Duration

This study will be conducted over an 18-month period to allow for subject enrollment, data collection, analysis, and manuscript preparation.

Activity		Month																
	1	2	3	4	5	6	7	8	9	10	11	12	13	14	15	16	17	18
IRB approval																		
Recruitment/enrollment																		
Data collection/ chart abstraction																		
Analysis																		

Manuscript preparation									

Analysis

Sample Size

We will enroll all consecutive patients who are eligible for inclusion in the 12-month enrollment period and consent to participation, up to 40 patients. An interim analysis will be performed after 20 patients are enrolled to assess means and variance of the primary outcomes, and reassess sample size.

Analytic Approach

Exploratory analysis methods will be used to describe the enrolled patient population, including mean and standard deviation for continuous variables such as length of hospital stay, sedation needs, and intubation as well as frequency and percentage for categorical variables such as STAT score and type of non-invasive PPV.

For the continuous outcomes of interest (duration of non-invasive respiratory support, length of hospital stay and sedation needs), either a two-sample t-test or non-parametric Mann-Whitney U test will be used to compare those patients who received NAVA or BiPAP. For categorical variables, either a chi-square test or Fischer's exact test will be used to compare the two groups. Additional regression analysis will adjust for procedure severity.

Statistical significance will be defined as p < 0.05.

5. Subjects

Subjects

We plan to enroll 40 subjects 0 to 12 months of age at time of cardiac surgery over a 1 year period.

Identification of Subjects, Recruitment, and Enrollment

Potential subjects will be identified by monitoring the cardiovascular surgery schedule, and eligibility will be confirmed by the provider. Patients who meet all of the inclusion criteria and none of the exclusion criteria will be approached for consent by study staff. Not all cardiac patients receive NIV support postoperatively, and the decision to provide NIV support is not made by the provider until after the surgery. This will happen either while the patient is intubated, or immediately following extubation. Written informed consent will be sought from parents/guardians. Assent will not be sought in this young patient population. Patients who enroll will be assigned a unique study ID. A log of enrolled subjects will be maintained, and will only be accessible by approved study staff. The target enrollment is 40 patients.

Inclusion Criteria:

- Postoperative cardiac surgery patients admitted to the CVCC
- Recommended for NIV respiratory support following extubation, per provider discretion
- 0-12 months of age

Exclusion Criteria:

- Tracheostomy in place at time of cardiac surgery
- Chronic lung disease
- Pre-operative non-invasive respiratory support

6. Study Procedures

Data Requirements

The data elements will be collected by the research study staff from the subject's electronic medical record. These will include:

- Demographic Data (name, date of birth, age at admission, admission date/time, cardiac diagnosis, comorbidities)
- Operative Data (surgeon, date of procedure, intubation/extubation date/time, date/time returned to CVCC)
- Adverse Event Information (description of event and day post-cardiac surgery that the event(s) took place)
- Medication Data (daily amounts of dexmedetomidine, fentanyl (total fentanyl and boluses of pca fentanyl), midazolam, morphine, lorazepam for up to 14 days postoperatively, date/time patient is on/off the above medications)
- Post-Operative Respiratory Support Data (type of non-invasive respiratory support used, date/time on off CPAP, date/time on/off biPAP/NAVA)
- Pain and Sedation Score Data (daily FLACC/SBS scores for up to 14 days postoperatively)
- Discharge Data (discharge date/time, length of hospital stay, survival at discharge, date/time of death [if applicable], cause of death [if applicable])

Visit Schedule

Eligible patients will be recruited during their admission to the CVCC. Upon enrollment, patients will be randomized to receive either NAVA or BiPAP. What respiratory modality the patient will receive will be determined by drawing a slip of paper from a sealed envelope. Following randomization and provision of respiratory support, patient care will be per standard care. Patient data will be only collected for the reference admission period. There will be no follow-up visits or activities required of the patient for this study following enrollment.

Drug/Device, Handling, Storage (If Applicable)

All devices in this study are currently used and stored in the CVCC. They will continue to be used as per CVCC SOPs.

7. Risks/Benefits

Potential Risks

Subjects will be randomized to respiratory support treatments that are already incorporated into standard care. The potential risks from these treatments are no more than those experienced as part of standard care. There is a risk associated with privacy of personal health information, and there is a risk of breach of confidentiality.

Methods to Minimize Risks

Both NAVA and BiPAP are non-invasive modalities that are safely used in standard care. Providers will follow SOPs for the use of NAVA and BiPAP support to minimize risks. If complications occur, standard care will be provided and patients will be treated accordingly. Electronic data will be stored on secure password-protected computers in limited access files, in a locked office suite. Any paper records will be stored in locked cabinets that only approved study staff have access to. This is a single-site study, and no identifiable patient data will be shared outside of the IRB-approved study staff. Any results from the study will be published in aggregate form, preventing any individual patient's data from being identified.

Potential Benefits

The subjects will not gain added benefit directly from this study, since the treatments provided will be consistent with standard care. This study will contribute to understanding how outcomes may vary with different modalities of respiratory support in this patient population.

Adverse Events

The research staff will document any adverse events that occur in the admission period for enrolled patients following provision of NAVA or BiPAP. Enrolled patients will be monitored in the CVCC, and standard care will be provided. Any unanticipated problems involving risks to the subjects or other (UPIRTSOs) will be reported to the IRB within 10 days.

Stopping Rules and Data Safety Monitoring Plan

The research interventions are both consistent with the standard of care for the study population. No stopping rules are planned.

8. Administrative Procedures

Patient Confidentiality

All study data will be stored on a secure password-protected computer in the locked research office. Patient study files will be stored in a locked cabinet within the research office. Subjects will be given a unique study ID number when entered into the RedCap study database.

Data Management

Data will be collected on paper documents and will be securely stored in a locked cabined within the research office. Only the research study team will have access to these paper documents. Once the data has been collected on the source documents, the data will be entered into a study-specific RedCap database, which is a secure network that is password-protected. All of the study data will be securely stored for up to 3 years or completion of the study and all subsequent publications and presentations of the study results.

9. References

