Appendix 2: Pain and Sedation Scales

Appendix 3: Study Schema

Appendix 4: Data Collection Forms

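### Aim 1's duration ends when staff who will in practice know the arm remove the device, and the visible text shows no coming-off criterion common to both arms and no recorded reason for stopping

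*Combined protocol and SAP*

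**What the plan says.** The document is a combined protocol and SAP. Section 4, Study Design, sets the course after assignment: "Following CPAP, enrolled subjects will be randomized to receive either NAVA or BiPAP, and their remaining clinical course will follow standard care". Section 6, Visit Schedule, repeats it: "Following randomization and provision of respiratory support, patient care will be per standard care".

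Aim 1 (section 4) compares duration of non-invasive respiratory support but does not define when it starts or ends. The relevant items under section 6, Data Requirements, are "date/time on off CPAP, date/time on/off biPAP/NAVA", abstracted from the medical record. The same list includes "intubation/extubation date/time", adverse events with the postoperative day, and date and time of death. It has no field for why support ended.

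The nearest references to a rule concern the unit's procedures. On devices, section 6 says "They will continue to be used as per CVCC SOPs". Section 7, Methods to Minimize Risks, says "Providers will follow SOPs for the use of NAVA and BiPAP support to minimize risks". Section 10 lists "Appendix 3: Study Schema" and "Appendix 4: Data Collection Forms", but our copy has only their titles. Section 7 also says that no stopping rules are planned; that refers to the trial, not to weaning.

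**The concern.** Randomisation balances the infants. It does not balance decisions made afterwards by people who know the assignment. If staff are readier to remove one device than the other, the off time moves even when recovery is identical. The regression for procedure severity (section 4, Analytic Approach) cannot remove this, because the behaviour follows the arm and not the operation.

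The direction is open. The stated hypothesis favours NAVA, which could prompt earlier removal. NAVA is also described as recently adopted in the unit, which could make staff slower to remove it.

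A second problem comes from the same data item. Support can end because the infant has recovered, or because the infant was reintubated, switched to another modality, or died. A bare off time records all of these as durations, and early failure then looks like a short, favourable one.

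At stake is what an Aim 1 difference would mean. Study Design says the aim is to learn whether one modality gives better outcomes. Off times alone do not separate faster recovery from a greater readiness to stop.

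**Working it through.** **Does the text support the claim?**

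1. *End of the duration.* Aim 1 gives no definition, so the end has to be inferred from the charted CPAP and BiPAP/NAVA times. Whether CPAP before or after the assigned device counts is not stated.
2. *Who decides.* Study Design and Visit Schedule both leave care after randomisation to standard practice.
3. *Knowledge of the arm.* No masking is described. The sealed envelope (Visit Schedule) conceals assignment only until it is opened. The background says NAVA is driven by a diaphragm signal from a nasogastric catheter. That staff will know the arm is an inference, but a safe one.
4. *Common criterion.* None is visible. The SOPs are cited for device use and risk reduction, and nothing says whether they cover coming off or treat both arms alike.
5. *Reason for stopping.* Reintubation, device change and death can be derived in part from listed items. Whether an infant came off because criteria were met, or for some other reason, cannot.

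**How large could it be?** The plan gives no durations, SD, effect size or power, so there is no figure to reproduce. What follows is illustration, and every input except the total of 40 and the 0.05 level is assumed.

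*Decision-only shift.* 20 per arm; time to readiness log-normal and equal in both arms (median 48 or 72 h, log-SD 0.6, 0.8 or 1.0); readiness-to-off gap gamma with mean 12 h and SD 6, 12 or 24 h; NAVA gap shortened by the shift; duration = max(readiness + gap, 1 h); t-test and Mann-Whitney, two-sided 0.05, counting only results that favour NAVA.

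| Shift | False significance favouring NAVA, range over cells |
|---|---|
| 0 h | 1.9-2.6% |
| 6 h | 3.0-9.6% (median about 5%) |

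At 6 h the total two-sided rejection rate is about 4-10%, against a nominal 5%.

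*Cross-check in SD units.* At a 48 h median the log-normal SD is 48 × exp(s²/2) × √(exp(s²) − 1): about 38 h at s = 0.6 and 104 h at s = 1.0. Ignoring the gap's own variance, 6 h is then 6/104 = 0.06 to 6/38 = 0.16 SD. For a shift of 0.1 SD, noncentrality is 0.1 × √(20/2) = 0.316 on 38 df, and rejection favouring NAVA is 4.9%, in line with the simulated median.

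*What the shift implies.* The share of NAVA infants removed before readiness is P(gap < shift). With gap SD 12 h the gamma is exponential, so at 6 h the share is 1 − exp(−6/12) = 39%. For gap SD 6 and 24 h it is 14% and 64%. At a 12 h shift the three shares are 57%, 63% and 74%, too extreme to guide a judgement, so no error rate is quoted for it.

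*Early failure.* If 2 of 20 NAVA infants have their duration capped at 12 h and nothing else differs, the mean falls by (2/20) × E[max(X − 12, 0)]. With a 48 h median for total duration the expectation is about 45, 54 or 67 h (log-SD 0.6, 0.8, 1.0), so NAVA looks about 4.5, 5.4 or 6.7 h shorter. Against an SD of 38-104 h this produces significance favouring NAVA in only about 3.5-6% of trials.

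**The case against.** The strongest reply is that this is a pragmatic comparison of two routine modalities. Masking at the bedside is hardly feasible with a dedicated catheter, the later course is deliberately left to standard care, and how clinicians respond to a device is part of what is compared. Actual duration under usual care is a legitimate endpoint. This stands, and it is why the endpoint should not change. It does not remove the need to say what a difference can be attributed to.

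A second reply is that the SOPs may already contain the criterion. This also stands. A reader might infer that the unit has no common rule. The documents do not support that, because the SOPs and Appendices 3 and 4 are not in our copy.

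A third is that the numerical effect is modest and wholly assumed. That is right: the 6 h figures centre on about 5%, and even they imply 14-64% of NAVA infants coming off before readiness. Nor does the protocol say that a reintubated infant will be scored as a short duration; that is what happens if only the off time is used.

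It is also tempting to treat the gap between readiness and removal as a test of staff behaviour. Under the same assumptions, its 95% CI excludes zero at a 6 h shift in about 87%, 37% or 17% of trials (gap SD 6, 12, 24 h). Readiness items are charted by unmasked staff and may respond to the modality, so a gap difference would not show its cause.

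**Conclusion.** The concern holds in a limited form. As visible, the plan gives Aim 1 a discretionary, unmasked end point, with no shown criterion common to both arms and no record of why support stopped. A difference between arms could partly reflect arm-dependent stopping, in either direction, and early failure can pass as a short duration.

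A reader might go further and infer that the Aim 1 result will be biased towards NAVA, or that duration is an invalid outcome. The documents support neither: no direction of bias is shown, and duration under usual care answers a sensible question.

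The illustrative size is about 3-10% false significance favouring NAVA for a 6 h shift, against about 2-3% with none. This rests on assumed 1:1 allocation, durations, gap and shift. The conclusion itself depends on none of these figures. It depends on two inferences: that duration ends at device removal, and that bedside staff know the arm. The trial can run without the change, but should make it because it is cheap and hard to reconstruct afterwards.

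**What to change.** Before the first infant is enrolled:

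1. Define the start and end of duration for Aim 1, and state whether CPAP time counts.
2. If the SOPs hold coming-off criteria common to both arms, cite them. If not, have the unit's clinicians agree one device-neutral set for both.
3. Add a reason-support-stopped field to the respiratory support data (met criteria, reintubation, switch of modality, death, other), derived from listed items where possible. Report it by arm, and do not read support that ended in failure or death as a favourable short duration.
4. State open-label removal as a limitation on attributing an Aim 1 difference to the modality.

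Actual duration remains the endpoint and the sample size is unchanged. Time from readiness to removal may be described by arm as an option, with no preset interpretation.

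The cost is one protocol paragraph, clinician agreement (unless the SOPs already suffice) and one abstracted field for up to 40 infants. Written criteria may slightly influence when staff stop support. The change reduces the problem and makes it visible; it does not remove it.

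### No visible rule says how reintubation or death enters NIV duration, or how death enters length of stay, so an early failure or death can score as a favourable short value

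*Combined protocol and SAP*

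**What the plan says.** Section 4 sets the direction. Aim 1 asks whether NAVA "is associated with a shorter duration of non-invasive respiratory support compared to conventional BiPAP", and Aim 3 whether it "is associated with reduced hospital length of stay compared to conventional BiPAP". The hypothesis counts shorter as better for both.

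The Analytic Approach in section 4 opens the comparison with "For the continuous outcomes of interest (duration of non-invasive respiratory support, length of hospital stay and sedation needs") and names a t-test or a Mann-Whitney test, with significance at p < 0.05. It then states: "Additional regression analysis will adjust for procedure severity". No censoring, competing-event or composite method is named.

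Section 6, Data Requirements, lists the raw material:

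- times of intubation and extubation, among the surgical items: "Operative Data (surgeon, date of procedure, intubation/extubation date/time, date/time returned to CVCC")
- device use: "type of non-invasive respiratory support used, date/time on off CPAP, date/time on/off biPAP/NAVA"
- complications: "Adverse Event Information (description of event and day post-cardiac surgery that the event(s) took place")
- survival at discharge and the time of any death

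Under Visit Schedule, collection is confined to the index admission. Section 7 adds that adverse events after the device starts are documented for that admission. Section 10 titles a study schema (Appendix 3) and data forms (Appendix 4), whose contents are not shown.

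**The concern.** The facts needed to recognise a failed course are mostly collected, but none is tied to the two durations. NIV can stop because the infant was weaned, was reintubated or died. A hospital stay can end in discharge or death. A test on plain durations treats these endings alike and reads the shorter value as the better one.

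If early failures or deaths are more frequent in one arm, that arm can look better on Aim 1 or Aim 3 because it did worse. Adverse-event and survival tables could show the imbalance beside the result but would not change the test. If the rule is chosen after the data are seen, the choice can also decide the direction of the result.

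**Working it through.** **Reading.** No visible text defines the start or end of NIV duration, says how repeat episodes combine, mentions reintubation, or scores a death. Providing standard care when complications occur (section 7) is not a scoring rule.

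**Plan's own figure.** There is none to reproduce. The target of 40 comes without power, effect size, SD or allocation ratio.

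**Simple arithmetic (assumed values).** Suppose 20 infants in an arm average 96 h, and k of them instead score 12 h through early failure. The arm mean is (12k + 96(20 − k))/20:

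- k = 1: (12 + 1824)/20 = 91.8 h
- k = 2: (24 + 1728)/20 = 87.6 h
- k = 4: (48 + 1536)/20 = 79.2 h

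**Simulation, Aim 1, single-episode scoring.** All inputs are assumed except the total of 40:

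- 20 infants per arm, two-sided 0.05, so 2.5% nominal in the wrong direction
- weaning time W lognormal with median 48 h and log-SD 0.8, the same in both arms
- failure time T exponential
- scored value Y = T if NIV fails, otherwise W
- 20,000 trials per scenario, so the simulation error of a 14.6% estimate is √(0.146 × 0.854/20,000) = 0.25 percentage points

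Chance that the arm with more failures is found significantly better, Mann-Whitney / t-test:

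| Failure rates (expected infants) | mean failure time 12 h | 24 h | 48 h |
|---|---|---|---|
| 20% v 10% (4 v 2) | 6.9% / 4.8% | 5.1% / 4.0% | 3.4% / 2.5% |
| 30% v 10% (6 v 2) | 14.6% / 8.9% | 9.1% / 6.6% | 4.4% / 3.7% |

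At 10% v 10% the Mann-Whitney figure is 2.1-2.3%, so there is no bias. With other inputs (median 72 h, failures at 2-24 h), Mann-Whitney gives 7.3% at 20% v 10% and 18.2% at 30% v 10%.

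**Aim 1, NIV hours summed over the admission** (30% v 10%, 12 h):

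- about 1.5% if every reintubated infant survives and returns to NIV
- about 2.6% if 20% of failures die and the rest return
- about 5.5% if only half return
- about 6.4% if half return and 20% of failures die

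**Aim 3.** Assumed stay lognormal with median 21 days and log-SD 0.7, and exponential time to death. Wrong-direction result, Mann-Whitney / t-test:

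| Deaths | mean time to death 7 days | 21 days |
|---|---|---|
| 10% v 0% (2 v 0) | 6.0% / 4.8% | 3.4% / 3.0% |
| 5% v 0% (1 v 0) | 3.8% / 3.4% | 2.9% / 2.5% |
| 5% v 5% | 2.5% / 2.4% | 2.5% / 2.0% |

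**Same data under a ranked rule.**

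- *Aim 1:* time from device start to final liberation, deaths before liberation worst. With a mean of 72 h invasive time and all survivors returning to NIV, 30% v 10% gives 0.2-0.4% in the wrong direction and 9.8-13.9% correctly against the worse arm.
- *Aim 1, half returning, no deaths, 12 h:* with invasive time averaging 24, 72 or 120 h, the wrong direction is 2.3%, 0.8% or 0.5%.
- *Aim 1, equal rates (10% v 10%):* 2.3% in the wrong direction and 2.5% in the other.
- *Aim 3, deaths ranked longest, 10% v 0%:* 0.7% in the wrong direction and about 7.5% correctly against the arm with the deaths.

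**The case against.** The strongest reply is that the harm on Aim 1 needs three things the documents do not state: single-episode scoring, failure rates that differ by arm, and failure that comes early. On/off times are collected across the whole admission, and nothing says that only the first episode counts. If episodes are summed and reintubated survivors return to NIV, the distortion largely disappears. Counts of reintubation and death beside the result would let a reader see an imbalance. All of this stands, and it limits the size. It does not supply a rule: summing is not specified either, and it does not cover infants who die or never return to NIV. For Aim 3 no episode reading is needed.

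A reader might infer more than the documents support:

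- *That the plan scores failures as successes, or that the trial is biased towards one device.* The plan is silent on scoring and gives no rates by arm.
- *That 14.6% is the expected error.* It belongs to a threefold difference in failure with very early failure, on assumed inputs.
- *That the data are missing.* Most are listed. What is missing is the link to the outcome.
- *That the sample-size review is compromised*, since "An interim analysis will be performed after 20 patients are enrolled to assess means and variance of the primary outcomes". Scoring 20% failures at a mean of 12 h as completed moves the mean from 66.1 to 55.3 h but the SD only from 62.6 to 60.3 h. Required n falls about 7% for a fixed absolute difference ((60.3/62.6)² = 0.93). It rises by about a third for a fixed relative one ((60.3/55.3)²/(62.6/66.1)² = 1.33). No clear direction of harm follows.

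**Conclusion.** The gap is real in the visible text and should be fixed; confidence is moderate. For Aim 3 it follows from a literal reading of the plan. For Aim 1 it depends on taking NIV duration as one episode's off time minus on time. The true size is unknown because the documents give no failure, death, weaning or stay figures.

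On the main assumed inputs, Mann-Whitney goes in the wrong direction in about 3-7% of trials at 20% v 10% failure, 4-15% at 30% v 10%, and 3-6% at 10% v 0% deaths, against 2.5% nominal. The t-test figures are lower. The conclusion would fall away if Appendix 3 or 4 already contains a scoring rule.

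**What to change.** Before any outcome data are examined, write into the SAP:

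1. **Aim 1.** Time from first start of the assigned NAVA or BiPAP to final liberation from both NAVA/BiPAP and invasive ventilation during the admission. A reintubated survivor keeps the full time. Infants who die before liberation rank worst, and any discharged on support rank just below them.
2. **Aim 3.** In-hospital deaths rank as the longest stay.
3. **Test.** Use Mann-Whitney, already named, for both, and put the same ranked outcomes into the severity-adjusted regression.
4. **Reporting.** Show raw NIV hours, reintubations and deaths by arm beside the result.

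The clock should not start at randomisation. Section 4 places that after CPAP and section 6 places it at enrolment, while section 5 allows the NIV decision during intubation. Invasive hours before the device starts could therefore be counted. In an assumed case with NIV 40% shorter in one arm and no failures, power falls from 48% to 33%, 23% or 17% when pre-NIV time averaging 24, 48 or 72 h is added. The SAP should also say how an infant who never starts the assigned device is handled.

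The cost is wording plus a check that the form captures every reintubation and extubation time in the admission, since these times are listed only among the operative items. The downside is that Aim 1 becomes a ranked outcome that includes invasive hours after NIV failure, so raw medians become descriptive. Other handling fixed in advance could also serve; this one keeps a test the plan already names.
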